### **Study Procedures**

Study procedures are illustrated in figure, below. The estimate of the number of participants reflects the expectation of attrition due to the length of the study. Potential participants will be screened online and over the telephone for inclusions and exclusions as outlined above. Informed consent, pretest, posttest, and follow-up testing sessions will be completed online. The online cognitive training protocols are largely completed online from the participants' home or other location of their choosing. All protocols include interactive components; in some cases this involves telephone calls and/or online discussion with research personnel. Total participation duration is 17 weeks. Data collection is planned to be completed within one year of REB approval.

Interested participants who replied by email to the study advertisement (see Appendix) will be emailed the information sheet portion (excluding the signature section) of the informed consent, and will be asked to complete the online screening form and phone screening interview (see script in Appendix). Eligible participants will then be emailed a link to an online pre-test assessment. As the bulk of the study will be taking place online, participants will accept provisions of the study through an online consent form.

Following completion of the pre-test assessment session, participants will be randomly assigned to one of four groups according to a blocked randomization scheme (stratified on age, gender, and education) created by a study team member unknown to participants or otherwise involved in data collection procedures. Participants will be informed of their group allocation by email and then begin the assigned program at their convenience, immediately following the completion of the pretest.

The intervention groups are as follows:

1. Online Memory and Aging Program: consists of weekly modules, and will take approximately 10 hours to complete over eight consecutive weeks. The content of the program includes: (a) the provision of factual information (i.e., about memory, age-related memory changes, lifestyle factors affecting memory, and memory strategies); and (b) memory intervention (i.e., practice and application of several evidence-based memory strategies). The information is delivered in a variety of formats, including videos, animations, interactive games, discussion boards, and live chats. As in the in-person MAP, participants will complete homework assignments in a Participant Workbook that will be mailed to them at the onset of the intervention. The program includes pre/post

assessment of knowledge, memory and lifestyle behaviours, and personal goals for reducing impact of memory change.

2. Test-retest group: This group will complete two assessments of knowledge, memory and lifestyle behaviours, and personal goals for reducing impact of memory change. These assessments will include a mix of online questionnaires and a telephone interview. Our prior research has shown equal attainment of personal goals for memory and lifestyle change in the face-to-face Memory and Aging program and a test-retest condition. Participants in this group will be offered the opportunity to complete the online Memory and Aging Program after study completion.
3. Online Goal Management Training: consists of 9 weekly modules composed of videos, interactive applets, and assignments, which take about approximately 20 hours total to complete. The program presents factual information about automatic processing, teaches strategies to stop and control automatic processes while maintaining focus on the current task goals and sub-goals, provides assignments that raise awareness into participants' own automatic processing and cognitive control, and provides games that allow participants to practice and build on the strategies acquired throughout the program. The program includes pre/post online assessment of cognition.
4. BrainHQ: is a commercial brain training platform that has a variety of short tasks. We will be using a customized training regimen that focuses on games designed to hone attention, memory, and brain speed. The program involves about an hour of training on this platform per week, which consists of a series of short games (5 min each) for half an hour at a time. The program includes pre/post online assessment of cognition.

#### Pre-/Post-test measures

Measures were selected based on previous findings from the in-person MAP and GMT evaluations. Most are standardized questionnaires and/or tasks, and most have been used previously, as noted below, and during preliminary pilot testing of the program. All measures will be administered during each testing session, and all will be administered online.

#### *Primary Outcome Measures:*

- Memory knowledge quiz, modified from Troyer (2001), will be used to quantify memory, lifestyle, and strategy knowledge
- Health Promoting Lifestyle Profile II (Walker, Sechrist, & Pender, 1987) will be used to quantify healthy lifestyle behaviours
- Memory strategy toolbox (Troyer, 2001) will be used to quantify application of strategies in memory-demanding everyday situations
- Multifactorial Metamemory Questionnaire (Troyer & Rich, 2002), will be used to quantify subjective memory abilities, satisfaction, and strategy use
- Dysexecutive functioning questionnaire (DEX; Burgess, Alderman, Wilson, Evans, & Emslie, H. (1996)
- Cognitive Failures questionnaire (CFQ; Broadbent, Cooper, FitzGerald, & Parkes, K. R. (1982)

#### *Secondary Outcome Measures (embedded within intervention conditions):*

- Conditions 1 and 2:

- Psychological Normalization Inventory will be used to quantify feelings of normalization of memory concerns
- Memory Impact Questionnaire and Patient-Specific Functional Scale (Horn et al., 2012) will be used to quantify the impact of memory changes on daily activities and self-image
- Intentions to seek medical attention modified from Wagner, Phillips, Radford, and Hornsby (1995) will be used to quantify change in intentions to seek medical attention pertaining to memory concerns
- Conditions 3 and 4:
  - Cambridge Brain Sciences online cognitive assessment (Hampshire et al., 2012)
  - Face-name memory task (Troyer et al., 2012)

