### **Statistical analyses**

Mixed-model ANOVAs will be used to examine pre-test and post-test scores on the outcome measures in the control and intervention groups. We will compare pre-test to immediate post-test and pre-test to follow-up post-test. The multiple test periods will be within-group repeated measures, and group assignment will be a between-groups variable. We expect significant interactions between group and pretest-posttest scores, with greater improvements over repeated test periods in the intervention group than the control.

This analysis will be done for each of the primary outcomes for both interventions. The same tests will be run on secondary outcomes to contrast the relevant intervention-control pair (e.g., GMT secondary outcomes measured/tested for GMT and BrainHQ, MAP secondary outcomes measures/tested in MAP and test-retest (waitlist) group.

No adjustments will be used for these primary and secondary *a priori* analyses.

We will also explore whether key variables including age, degree of engagement with the program, presence of subjective cognitive impairment, and computer familiarity covary with the effects of the intervention, and if so control for them by adding them as covariates in our statistical models.

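### The documents conflict on when the secondary baseline is taken; on the more natural reading it follows disclosure of the arm, so the group-by-time test would use a baseline that randomisation does not protect

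*Combined protocol and SAP*

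**What the plan says.** Study Procedures sets the order of events: "Following completion of the pre-test assessment session, participants will be randomly assigned to one of four groups". Disclosure follows: "Participants will be informed of their group allocation by email and then begin the assigned program at their convenience". That sentence goes on to say that the start comes directly after the pre-test.

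The secondary outcomes have their own list, headed "Secondary Outcome Measures (embedded within intervention conditions". Conditions 1 and 2 (MAP, test-retest) receive normalization, memory impact and intention to seek medical attention. Conditions 3 and 4 (GMT, BrainHQ) receive an online cognitive battery and a face-name task. For GMT and BrainHQ alike, the description of the arm states: "The program includes pre/post online assessment of cognition". MAP is also described as containing its own pre/post assessment. For the test-retest arm: "These assessments will include a mix of online questionnaires and a telephone interview".

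The section Pre-/Post-test measures says something different: "All measures will be administered during each testing session, and all will be administered online".

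Under Statistical analyses, the secondary outcomes belong to the relevant pair only (for example, "GMT secondary outcomes measured/tested for GMT and BrainHQ"). They receive the same mixed-model ANOVA as the primary outcomes, and the effect of interest is the interaction: "We expect significant interactions between group and pretest-posttest scores". The section does not say which assessment is the secondary baseline.

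**The concern.** A participant has no condition until randomised. If the secondary measures are delivered inside the condition, and differ between the two pairs, their first administration comes after the participant has been told the arm by email. Such a score is no longer a pre-randomisation covariate, because knowledge of the allocation can move it.

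The pair most exposed is MAP versus test-retest. One arm knows it is getting a programme and the other knows it must wait, and the measures are self-reports of feelings, impact and intentions. Reduced intention to seek unneeded medical care is one of the MAP aims under Objectives, and its measure appears only in this secondary set. The interaction test would read an arm difference created at baseline, and absent later, as a difference in change. It could produce a false benefit or hide a real one.

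**Working it through.** **Step 1: set the statements side by side.**

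| Section | Points to |
|---|---|
| Study Procedures: pre-test, then randomisation, then disclosure | fixes the order of events |
| Secondary Outcome Measures: embedded, split by condition | baseline after disclosure |
| Arm descriptions: pre/post assessment within MAP, GMT and BrainHQ | baseline after disclosure (weaker evidence) |
| Statistical analyses: measured and tested in the relevant pair | baseline after disclosure |
| Pre-/Post-test measures: all measures at each session, all online | baseline before randomisation |

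The last row also conflicts with the telephone interview in the test-retest arm. The two accounts cannot both be followed. The embedded one has more support, but no sentence states the timing outright.

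**Step 2: what a baseline-only shift does.** With two arms and two time points, the group-by-time test is a two-sample test on change:

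difference in change = (difference in post-test means) − (difference in baseline means).

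If there is no programme effect and one arm's baseline moves by d relative to the other, with no carry-over to post-test, the expected difference in change is d in size. If the shift persists equally to post-test, it cancels.

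**Step 3: size.** The documents give 200 participants and no allocation ratio, alpha, SD, correlation or dropout rate, so the 200 cannot be re-derived. Assumptions: equal allocation, 200/4 = 50 per arm; two-sided 5%; equal SDs; pre-post correlation ρ of 0.5 to 0.8; shift d confined to baseline.

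- SD of change = √(2(1−ρ)) in baseline SD units.
- SE of the difference in change = SD of change × √(2/n).
- False-positive rate = P(Z > 1.96 − d/SE) + P(Z < −1.96 − d/SE).

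Example, ρ = 0.5: SD of change = 1.0 and SE = 1.0 × √(2/50) = 0.20. For d = 0.2, d/SE = 1, so the rate is P(Z > 0.96) + P(Z < −2.96) = 0.170.

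| n per arm | ρ | d = 0 | d = 0.1 | d = 0.2 | d = 0.3 |
|---|---|---|---|---|---|
| 50 | 0.5 | 0.050 | 0.079 | 0.170 | 0.323 |
| 50 | 0.7 | 0.050 | 0.099 | 0.252 | 0.491 |
| 50 | 0.8 | 0.050 | 0.124 | 0.353 | 0.660 |
| 40 | 0.5 | 0.050 | 0.073 | 0.145 | 0.269 |
| 40 | 0.8 | 0.050 | 0.109 | 0.293 | 0.564 |

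The 40-per-arm rows assume 20% attrition; the plan expects attrition but gives no rate. A simulation with 20,000 runs per setting agrees: at n = 50 and d = 0.2 it gives 0.170, 0.248 and 0.344 for ρ = 0.5, 0.7 and 0.8. With no shift, the rate across all simulated settings is 0.048 to 0.052.

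**Step 4: the other direction, and adjustment.** At ρ = 0.7 and n = 50, power for a true 0.4 SD effect is 0.733 with no shift and 0.252 with an opposing 0.2 SD shift. Baseline-adjusted ANCOVA reduces the bias to ρ × d but does not remove it: at d = 0.2 and n = 50 the false-positive rate is 0.089 (ρ = 0.5) to 0.266 (ρ = 0.8).

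**The case against.** The strongest reply is that the documents never put the secondary baseline after randomisation in so many words. One sentence gives all measures at each testing session, and the pre-test session precedes randomisation; on that reading there is no defect. Study Procedures also refers to a figure that is missing from the text available here and may show the timing. This stands. A reader might infer that the post-allocation baseline is a fact of the design, but the documents support it only as the more natural of two conflicting readings.

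Second, the programme descriptions are weaker evidence than they look. The MAP assessment is described as covering knowledge, memory and lifestyle, which are primary-outcome constructs, so that description may only list what a participant in the arm undergoes. This also stands; the case rests mainly on the secondary-outcome heading, its split by condition, and the pairwise measurement in the SAP.

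Third, a reader might infer that any allocation effect on the baseline passes in full into the result. That needs a shift that differs between the paired arms and is confined to baseline. For GMT versus BrainHQ, two active programmes with cognitive tasks, no clear mechanism for a differential shift is apparent.

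Fourth, it is tempting to add that people who never open a programme would lack a baseline in one arm only. They may well miss the embedded post-test too, and in the GMT–BrainHQ pair both arms are programmes. The documents do not allow this to be sized, and the point does not rely on it.

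**Conclusion.** The concern holds in conditional form. The documents contradict themselves on when, and by what mode, the secondary baseline is taken. On the embedded reading, the planned interaction test uses a baseline that randomisation does not protect. The risk lies mainly in the MAP versus test-retest self-reports and is weaker for the GMT versus BrainHQ tasks. The primary outcomes are not described as embedded and are not affected.

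The figure of about 17–35% for a 0.2 SD shift is a sensitivity result under the assumptions in the working. It is not an estimate of this trial's error rate: the documents give no shift size and no evidence that a shift occurs. Confidence is high that the passages conflict and moderate that the baseline would in practice follow disclosure. The matter is still more than missing detail, because a simple change in timing closes the route to bias.

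**What to change.** Reconcile Study Procedures (including the arm descriptions), Pre-/Post-test measures, Secondary Outcome Measures and Statistical analyses. Suggested content:

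- *Every participant completes the online secondary measures for all four conditions in the pre-test session, before randomisation.* Later administrations may remain specific to the condition.
- *The pre-randomisation score is the only baseline used in the secondary analyses.*
- *Each measure is administered in the same mode in both arms of a pair.* Any change of setting between pre-test and post-test then applies to both arms alike.
- *For any measure that must stay embedded, for example one taken by telephone interview, post-test scores are compared between the randomised arms without the embedded baseline.*

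With a pre-randomisation baseline, the expected between-arm shift is zero and the false-positive rate returns to the nominal 5%. The cost is protocol wording and a somewhat longer online pre-test, since each participant also completes the other pair's measures once; this is what the section on pre-/post-test measures already implies. Extending a telephone-based measure to all 200 participants would take staff time, which is why the post-test-only option is offered. That option can cost power: for a true 0.4 SD effect at 50 per arm it has power 0.516, against 0.733 for an unbiased change analysis at ρ = 0.7. At ρ = 0.5 the two are equal.

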## **Statistical Analysis Plan**

### **Data management**

An anonymized database will be created to link identifying participant information to the outcome measure data. Participants will be given unique ID numbers, and information that links identifying information to participant ID numbers will be stored on a password-protected secure server.

### **Statistical analyses**

Mixed-model ANOVAs will be used to examine pre-test and post-test scores on the outcome measures in the control and intervention groups. We will compare pre-test to immediate post-test and pre-test to follow-up post-test. The multiple test periods will be within-group repeated measures, and group assignment will be a between-groups variable. We expect significant interactions between group and pretest-posttest scores, with greater improvements over repeated test periods in the intervention group than the control.

This analysis will be done for each of the primary outcomes for both interventions. The same tests will be run on secondary outcomes to contrast the relevant intervention-control pair (e.g., GMT secondary outcomes measured/tested for GMT and BrainHQ, MAP secondary outcomes measures/tested in MAP and test-retest (waitlist) group.

No adjustments will be used for these primary and secondary *a priori* analyses.

We will also explore whether key variables including age, degree of engagement with the program, presence of subjective cognitive impairment, and computer familiarity covary with the effects of the intervention, and if so control for them by adding them as covariates in our statistical models.

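### Attrition is expected, but the mixed-model ANOVAs come with no stated population, estimator or missing-data assumption; a REML mixed model on all randomised participants, using the pre-test, would be a cheap improvement

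*Combined protocol and SAP*

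**What the plan says.** The protocol section Study Procedures gives a total participation of 17 weeks and adds: "The estimate of the number of participants reflects the expectation of attrition due to the length of the study". No rate is given. Testing has three occasions: "Informed consent, pretest, posttest, and follow-up testing sessions will be completed online". Allocation comes after the first of them: "Following completion of the pre-test assessment session, participants will be randomly assigned to one of four groups", by a blocked scheme "stratified on age, gender, and education".

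The SAP section Statistical analyses plans: "Mixed-model ANOVAs will be used to examine pre-test and post-test scores on the outcome measures in the control and intervention groups". It continues: "We will compare pre-test to immediate post-test and pre-test to follow-up post-test". On structure it says: "The multiple test periods will be within-group repeated measures, and group assignment will be a between-groups variable". Arm pairs are named for secondary outcomes: "The same tests will be run on secondary outcomes to contrast the relevant intervention-control pair". The section also rules out adjustments for the primary and secondary analyses, without saying whether this means multiplicity or covariates. Engagement with the program appears only as a variable to explore.

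The other SAP section, Data management, deals with storage and linkage of data. Nowhere do the documents give an analysis population, an estimator, a covariance structure, a missing-data assumption or a sensitivity analysis.

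**The concern.** The term mixed-model ANOVA has two common meanings. One is the classical mixed-design ANOVA (one within-participant factor, one between), which the SAP's description fits well. As usually run, it needs complete data and drops anyone lacking a visit in the analysis. The other is a linear mixed model fitted by likelihood, which uses every observed visit.

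The SAP also leaves open whether there are two two-period ANOVAs or one three-period ANOVA. Under the first, a person missing only follow-up still counts at post-test. Under the second, that person's observed post-test is lost too. Two analysts following the plan could therefore report different estimates from the same data, and the choice could be made after drop-out by arm is known.

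Two things are at stake: some lost precision, and bias if loss is related to scores and differs by arm. Unequal drop-out rates alone do not cause bias.

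**Working it through.** **Inputs.** From the documents: 200 participants, four groups, pre-test before randomisation, three test occasions. Assumed, because the documents give none of these: equal allocation (200/4 = 50 per arm), SD 1 at each visit, correlation ρ = 0.7 between any two visits, two-sided 5% level, true effect 0.4 SD for power. The plan states no power or bias figure, so there is nothing to reproduce first.

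**Bias (no true effect).** The control arm loses 10% at random. The active arm loses 20% or 30%, with a logistic drop-out slope of 0.5 or 1.0 per SD of the variable that drives loss. Let m be the shift, in SD, in the mean of that variable among those who stay. Integrating the logistic curve over a normal distribution gives:

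| Slope | 20% lost | 30% lost |
|---|---|---|
| 0.5 | m = 0.096 | m = 0.143 |
| 1.0 | m = 0.173 | m = 0.253 |

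The size of the bias in the group difference in change is then as follows. The sign depends on who leaves.

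- *Loss before post-test, related to the pre-test score.* Completer ANOVA: (1 − ρ)m = 0.3 × 0.096 = 0.03 to 0.3 × 0.253 = 0.08 SD, at both visits. Likelihood model: about 0, because the pre-test is observed for everyone randomised.
- *Loss before post-test, related to unobserved pre-post change.* Completer ANOVA at post-test: √(2(1 − ρ)) × m = 0.775 × (0.096 to 0.253) = 0.07–0.20 SD; half of that at follow-up, 0.04–0.10 SD. Likelihood model at post-test: (1 − ρ²)/√(2(1 − ρ)) × m = 0.658 × m = 0.06–0.17 SD; by simulation, 0.03–0.07 SD at follow-up. It removes only 1 − 0.658/0.775 = 15% of the post-test bias.
- *The same, but leavers gave a post-test first.* Likelihood bias is about 0 at both visits. The completer ANOVA keeps 0.04–0.10 SD at follow-up, and is biased at post-test only under the three-period reading.
- *Loss before post-test, related to the unobserved post-test level.* Completer ANOVA: (1 − ρ)m = 0.03–0.08 SD at post-test and about 0 at follow-up. Likelihood model: (1 − ρ²)m ≈ 0.05–0.13 SD at post-test and 0.02–0.055 SD at follow-up (by simulation). The likelihood model is worse here.
- *Random loss.* About 0 for both.

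Simulation with 1,000,000 per arm agrees with these values to within about 0.005 SD. Constraining the pre-test means to be equal does not alter the large-sample bias, since randomisation already makes them equal in expectation.

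At 50 per arm, a bias of 0.076 SD with 45 v 35 completers has SE √(0.6 × (1/45 + 1/35)) = 0.175. The type I error is then about 7% instead of 5%.

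**Power (random loss, effect 0.4 SD).** Change-score analysis: SE = √(2 × 2(1 − ρ)/n), power = Φ(0.4/SE − 1.96).

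- n = 50: SE 0.155, power 73%.
- n = 40 (20% lost): SE 0.173, power 64%.
- n = 35 (30% lost): SE 0.185, power 58%.

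Keeping incomplete cases in a likelihood model raises simulated follow-up power from 63% to 64–66% (20% lost) and from 58% to 59–61% (30% lost), a gain of 1–4 points.

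Using the pre-test as a covariate: SE = √(2(1 − ρ²)/n). At n = 40 this is √(2 × 0.51/40) = 0.160, giving Φ(2.505 − 1.96) = 71%, against 64% for change. This is the larger gain, and it does not depend on drop-out.

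**The case against.** The strongest reply is that the plan excludes nobody. A reader might infer that it sets out a completers-only analysis. The documents do not support that: group assignment is the between-groups factor, which points to analysis as assigned, engagement is only explored, and mixed-model may already mean a likelihood model. What stands is that the plan does not say whether people without a later visit are kept.

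The illustration also leans towards larger effects, since every informative case puts selective loss in the active arm alone. If both arms lose the same share by the same mechanism, bias is about 0 for both methods. If both arms lose selectively on change, at 20% v 10% and slope 1.0, completer bias at post-test falls from 0.13 to 0.06 SD. This objection stands, and the figures show only what could happen.

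A mixed model is also not uniformly better, as the case of loss related to the unobserved post-test level shows. That stands too, and is why a sensitivity analysis belongs in the proposal.

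Finally, a reader might infer that the test-retest group has no follow-up, because its description mentions two assessments. The documents do not support singling it out. All four arm descriptions mention only pre and post assessments, while Study Procedures and Statistical analyses state the follow-up for the study generally.

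**Conclusion.** The point holds as a cheap improvement of minor to moderate weight. Attrition is expected, the SAP's description fits an ANOVA that usually drops incomplete cases, and the plan does not settle the matter. A better method is available at almost no cost, because every randomised participant should have a pre-test.

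A reader might go further and conclude that the trial's results will be biased by a known amount, or that a mixed model would cure the problem. Neither follows. The documents give no drop-out rate or reason by arm, so size and direction are unknown. The 0.03–0.08 SD v about 0 for pre-test-related loss rests on 50 per arm, correlation 0.7, 20–30% lost and selective loss in the active arm only. The retention gain of 1–4 power points and the covariate gain (71% v 64% at 40 per arm) also rest on the assumed correlation and the 0.4 SD effect. If a likelihood model is already meant, the estimator needs only to be named.

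**What to change.** In the SAP section Statistical analyses:

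- Analyse all randomised participants as assigned, whatever their engagement, with a REML linear mixed model using all observed visits, categorical time, group × time and an unstructured covariance.
- Because randomisation follows the pre-test, constrain the pre-test means to be equal across arms, or adjust for the pre-test. Include the stratification factors (age, gender, education). If the sentence ruling out adjustments refers to multiplicity, say so; as it stands it could be read as barring these covariates.
- Report the group difference at post-test and at follow-up. State the missing-at-random assumption, and report drop-out by arm and visit.
- Add one simple sensitivity analysis for data not missing at random, for example shifting imputed scores separately by arm over a range fixed in advance.
- Keep the comparators the plan intends. The pairs are named only for secondary outcomes, and Objectives refers to control groups in the plural, so the sponsor should confirm those for the primary outcomes.

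The cost is a few sentences of SAP text and a little more analysis work, with no extra participants or visits. The downside is reliance on missing-at-random. The model removes only part of the bias if early loss depends on unobserved change, and can be more biased than the ANOVA if loss depends on the unobserved post-test level.

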## **Method**

### **Study population**

200 healthy community-dwelling older adults will be recruited by newspaper and online advertisements (see Appendix).

Inclusion criteria:

[figure not shown]
- (a) Age 60+
- (b) Available to participate in all testing and intervention sessions and access to a computer
- (c) Computer familiarity
- (d) Cognitive complaint/concern/frustration

Exclusion criteria:

- (a) Health conditions with major effects on cognition, including a current or previous history of stroke, brain surgery, or diagnosed neurological disorder;
- (b) Dependence in instrumental activities of daily living
- (c) Cognitive impairment, defined as performance below cutoff for cognitive impairment on a standardized cognitive screening measure, the modified Telephone Interview for Cognitive Status (Welsh et al., 1993)
- (d) Affective impairment, defined as performance below cutoff for depression on standardized depression screen, the Geriatric Depression Scale (Yesavage et al., 1983)

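### Randomisation is stratified on age, gender and education, but the a priori models omit all three; if these factors predict change, the group-by-time tests are conservative and lose some power

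*Combined protocol and SAP*

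**What the plan says.** Under Study Procedures, "participants will be randomly assigned to one of four groups according to a blocked randomization scheme (stratified on age, gender, and education"). The cut-points, block size and allocation ratio are not given.

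Under Statistical analyses, the a priori models are mixed-model ANOVAs with two factors: "The multiple test periods will be within-group repeated measures, and group assignment will be a between-groups variable". The effect of interest is the interaction: "We expect significant interactions between group and pretest-posttest scores, with greater improvements over repeated test periods in the intervention group than the control". The contrasts are set out as pairs: "We will compare pre-test to immediate post-test and pre-test to follow-up post-test". The same analysis is to be run for each primary outcome, and for the secondary outcomes within the relevant intervention-control pair.

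The last paragraph of that section is exploratory. It names age among several variables whose relation to the intervention effect will be examined, and provides for adding a variable as a covariate if such a relation is found. Gender and education are not named there or elsewhere in the analysis plan. No reason is given for leaving the stratification factors out of the a priori models.

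**The concern.** Stratified blocking forces the arms to be nearly alike on the stratifiers, so chance differences between arms due to those factors are largely removed from the treatment comparison. A model that omits the factors still counts their contribution in its residual variance. Where the factors predict the quantity being analysed, the model's standard error then exceeds the true sampling variation. Intervals are too wide, the type I error falls below its nominal level, and power that the design has earned is not used.

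The plan has two further weaknesses. Adjustment for a design factor is left to depend on the data, and for only one of the three factors by name, so adjusted and unadjusted versions of the same result could both be defended. The documents also contain no power calculation, so one cannot assume that there is power to spare.

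**Working it through.** **Inputs from the documents.** Total sample: "200 healthy community-dwelling older adults will be recruited by newspaper and online advertisements". Groups: four. Dropout: expected, with no rate ("The estimate of the number of participants reflects the expectation of attrition due to the length of the study"). Tested effect: group by time, for pre-test versus immediate post-test and pre-test versus follow-up.

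**Assumptions, none of them in the documents.** Equal allocation, so 200 / 4 = 50 per arm. Two-sided alpha of 0.05. Effect d = 0.5 SD of change. R², the share of variance in *change* explained by the stratifiers, of 0 to 20%.

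The figure of 200 comes without effect size, SD, alpha or power, so there is no planned figure to reproduce.

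**Step 1: what the planned test compares.** With two time points, the group-by-time interaction equals a between-group comparison of change scores. Whatever age, gender and education contribute to a person's stable level cancels in the change. R² must therefore refer to change, not to level.

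**Step 2: reported and true standard error.** With s the SD of change and n per arm, the unadjusted model reports s·√(2/n). After stratified allocation with complete data, the true value is close to s·√(2(1−R²)/n). The ratio of reported to true is 1/√(1−R²), and the actual type I error is 2[1 − Φ(1.96/√(1−R²))].

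**Step 3: power.** At n = 50, √(2/50) = 0.2, so d/SE = 0.5/0.2 = 2.5.
- Unadjusted: Φ((2.5 − 1.96)/√(1−R²))
- Adjusted: Φ(2.5/√(1−R²) − 1.96)

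| R² of change | Interval too wide by | Actual type I error | Power, unadjusted | Power, adjusted | Gain (points) |
|---|---|---|---|---|---|
| 0% | 0% | 5.0% | 70.5% | 70.5% | 0 |
| 2% | 1.0% | 4.8% | 70.7% | 71.4% | 0.7 |
| 5% | 2.6% | 4.4% | 71.0% | 72.7% | 1.7 |
| 10% | 5.4% | 3.9% | 71.5% | 75.0% | 3.5 |
| 20% | 11.8% | 2.8% | 72.7% | 79.8% | 7.1 |

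Example at R² = 10%: √0.9 = 0.949; unadjusted Φ(0.54/0.949) = Φ(0.569) = 71.5%; adjusted Φ(2.635 − 1.96) = Φ(0.675) = 75.0%.

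**Step 4: simulation check.** Setting: 100 participants per intervention-control pair, eight strata from three binary factors, blocks of 4, 8,000 trials, effect 0.56 SD of change, strata explaining 30% of mean level.
- Strata explain none of change: the two analyses agree. Model SE is 0.178 against 0.179, type I error 5.3% against 5.4%, and power 79.5% in both.
- Strata explain 10% of change: the unadjusted model SE is 0.179 against a true 0.171, and type I error is 4.2%. Power is 80.1% unadjusted and 83.1% adjusted.
- Strata explain 20% of change: unadjusted type I error is 2.9%. Power is 81.9% unadjusted and 87.1% adjusted.

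**Step 5: dropout.** Random dropout partly undoes the balance. In a simulation of 200 people in four arms with R² of change at 20%, losing 20 to 30% at random put the unadjusted type I error at about 3.4 to 3.9%, against 2.8% in the complete-data table.

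**The case against.** The strongest reply is that the planned test is already a change-score comparison. A reader might infer from the omission that every interval in this trial is too wide and that power is certainly lost. The documents do not support that. The stratifiers matter only if they predict change, no figure for this is given, and at zero the planned and adjusted tests are the same. This stands, and the point has to be conditional.

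Three smaller replies also stand in part.
- Dropout is expected and would soften the conservatism, so the complete-data type I errors mark the far end.
- The list of exploratory variables is illustrative, so gender and education are not excluded from it. But that route depends on the data and is triggered by a relation with the intervention effect, which is not the same as adjusting for a design factor.
- Any error is on the conservative side. False positives are not inflated and the estimate is not biased.

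A reader might also take "No adjustments will be used for these primary and secondary" as an explicit refusal of covariates. The sentence follows a list of many tests on many outcomes and may well refer to multiplicity. It is ambiguous and is not relied on here.

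What the replies leave untouched is that the trial randomises by three factors and does not analyse by them. The plan itself treats age as a possible modifier of the effect. If that is so, age will generally predict change in the treated arm, and R² would not be zero.

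**Conclusion.** The point holds as a conditional weakness in efficiency and pre-specification, not as a failure of validity. The a priori models omit all three stratification factors. If these explain up to 10% of the variance in change, standard errors are up to about 5% too large and the power lost is up to about 3.5 points. The loss becomes material near 20%, at about 7 points. If they explain none, there is no loss. These sizes rest on assumed equal allocation, complete data, a two-sided 5% level, an effect of 0.5 SD of change, and an R² for which the documents offer no guide. The change is still worth making, because it costs almost nothing and settles in advance an adjustment that is now left to exploration.

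**What to change.** In Statistical analyses, state that every primary and secondary group comparison includes age, gender and education, either as categorised for stratification or with age and education in years, whatever their significance. Use one of two forms and name it:
- In the repeated-measures model, include each factor **crossed with test period**. Main effects alone leave the group-by-time test unchanged.
- In a model of the post-test score given the pre-test score, enter the three factors as main effects.

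Keep the exploratory paragraph for the other variables, and take age out of its conditional rule for covariate adjustment. In the same edit, say whether the sentence about no adjustments means covariates or multiplicity.

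The cost is a sentence or two in the plan and a few degrees of freedom. No new data are needed, since the three factors must be known before a participant can be randomised.
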